
Study Context & Rationale
	
Detection and intervention before psychosis develops, when individuals are at clinical high risk for psychosis (CHR), could attenuate, postpone, or even prevent the conversion to psychosis and improve individuals' clinical and functional outcomes. The Accelerating Medicines Partnership in Schizophrenia (AMP SCZ) is a US-based public-private program with the overall aim of generating tools that will considerably improve success in developing early stage interventions for patients who are at risk of developing schizophrenia and other psychotic disorders. The current AMP SCZ partners include government partners (NIH, FDA, European Medicines Agency), industry partners (Boehringer Ingelheim, Janssen, Otsuka), and non-profit partners (American Psychiatric Association Foundation, National Alliance on Mental Illness, One Mind, Schizophrenia and Psychosis Action Alliance, Wellcome). AMP SCZ aims to develop measures that further define early stages of risk and predict the likelihood of progression to psychosis and other clinical outcomes (e.g., non-remission of CHR status, functioning, anxiety, depression, and substance use disorders), and define targets for treatment development. Such tools will enable clinical trials to test new pharmacological interventions that may prevent or delay the onset of psychosis.
 
In order to realise the aims of AMP SCZ, NIMH released a Research Funding Announcement (RFA) in December 2019 to fund CHR Research Networks to collect multimodal data in large samples of CHR patients. Two international networks were funded: PRESCIENT, led by researchers based at Orygen (PI [name]), and ProNET, led by US-based researchers (PI [name]). The current Human Research and Ethics Committee submission relates to the PRESCIENT Research Network. Additionally, a Data Processing, Analysis, and Coordinating Center (DPACC; PI [name], Harvard University) was funded, with the purpose of integrating and analysing data from new and key existing clinical high risk cohorts, including the AMP SCZ cohort.
 
Findings from AMP SCZ will enable researchers to develop algorithms that predict the course of illness for clinical high risk individuals, allowing for early intervention and testing of treatments that may prevent the development of schizophrenia and other psychotic disorders and reduce their impact. All AMP SCZ data and analyses will be made publicly available through the NIMH Data Archive. Through rapid data sharing and integrated, collaborative research, AMP SCZ will enable proof-of-principle clinical trials to test tools and hypotheses that emerge from the initiative.

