---	---

Primary Objectives
	
1. CHR Network Consolidation: Use the Australian Early Psychosis Collaborative Consortium (AEPCC) national platform to consolidate a network of CHR recruitment centres organised according to a ‘hub and spoke’ model, with Orygen functioning as the central hub with 1 Australian and 9 non-Australian clinics as spokes. The network will: recruit a large sample of CHR patients (n=937) and a healthy control (n=250) sample; implement repeated multimodal assessments; map trajectories and outcomes over a 2 year period (conversion to psychotic disorder, persistent and incident non-psychotic disorders, non-remission of CHR status, persistent negative symptoms, psychosocial functioning, full recovery). This network of CHR recruitment centres will provide the clinical research infrastructure for future treatment trials in this clinical population informed by findings from the current program of work.
 
2. Prediction: In collaboration with the NIMH Steering Committee and the DPACC, the PRESCIENT dataset will be used to:
 
2a. Test the external validity of existing and forthcoming prediction models in the field (e.g., NAPLS, EU-GEI, PRONIA, PSYSCAN).
 
2b. Implement the model with strongest performance as an online risk calculator that can be calibrated for service setting (primary vs specialist settings) and availability of type of data (e.g. clinical data alone, clinical data plus neurophysiological data, polygenic risk score, etc).
 
2c. Use the full AMP SCZ dataset (combined PRESCIENT and ProNET data) to develop new, more refined prediction models and risk calculators using recent theoretical and methodological advances (e.g., dynamic prediction, probabilistic multimodal modelling) and a range of biomarkers. These tools will be of clinical utility in decision making about stepping interventions up/down as risk is assessed over time (clinical trajectory, treatment response) and in response to incoming biomarker information, as well as guide stratification of patients in future clinical trials.
 
3. Validation: Internally and externally validate the prediction models generated using the AMP SCZ dataset. This will test the robustness, replicability and generalisability of the models’ performance.
 
The national and international network of sites and research specialisation will provide the clinical research infrastructure for future treatment trials in this clinical population informed by findings of the current program of work.

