5.1.1. The Need for New Therapies

Detection and intervention before psychosis develops, when individuals are at clinical high risk for psychosis, could attenuate, postpone, or even prevent the conversion to psychosis and improve individuals' clinical and functional outcomes. AMP SCZ aims to develop measures that further define early stages of risk and predict the likelihood of progression to psychosis and other clinical outcomes. Such tools will enable clinical trials to test new pharmacological interventions that may prevent or delay the onset of psychosis.

AMP SCZ partners will work towards the shared mission of discovering promising biological markers that can help identify those at risk of developing schizophrenia as early as possible, track the progression of symptoms and other clinical outcomes, including anxiety, depression, and substance use disorders, and define targets for treatment development.

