5.2. Clinical High Risk for Psychosis: Background and Significance

The 'clinical high risk' (CHR) for psychosis criteria prospectively identify young people at risk of psychotic disorders (i.e., individuals who may be in the prodromal phase of psychosis)^{1,2}. The CHR criteria have been well-validated, with approximately one third of CHR individuals converting to a psychotic disorder over a 3-year period, a rate considerably higher than in the general population and other clinical populations^{1,3,4}. The CHR approach introduced a new paradigm to psychosis research and has been remarkably influential, with the Diagnostic and Statistical Manual of Mental Disorders-5 (DSM-5) including 'Attenuated Psychosis Syndrome', based on the CHR criteria, as a condition requiring further research⁵.

There is *substantial heterogeneity* in clinical trajectories in the CHR population. For example, in a recent analysis of data from our multisite international trial of omega-3 fatty acids ('Neurapro'⁶) we identified 17 different trajectories in this clinical group⁷ (see Fig 1 for the most common trajectories). The field is currently unable to reliably identify these trajectories early on, particularly at an individual patient level. The models to date (using clinical, neurocognitive, neuroimaging, neurobiological and genetic data) have yielded only modest predictive value for conversion to psychotic disorder and other outcomes^{3,8,9}. This presents a challenge for targeted intervention and developing robust aetiological models. There is also now increased recognition of the CHR phenotype as a syndrome in itself, rather than merely being a risk syndrome, supported by meta-analytic evidence that CHR patients are characterised by consistent and large impairments in functioning and reduction in quality of life similar to those in other coded psychiatric disorders¹⁰⁻¹². In addition, there is strong evidence that CHR status is a marker of illness severity and poor prognosis transdiagnostically¹³⁻¹⁵. Therefore, enhancing prediction of the full spectrum of outcomes in the CHR population (conversion to psychotic disorder, persistent and incident non-psychotic disorders, non-remission of CHR status, poor functioning etc.) is of critical importance^{16,17}. Enhanced predictive accuracy of these outcomes would be a substantial step forward in facilitating treatment development and developing aetiological models of psychosis and psychiatric disorders more broadly.

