5.5. Study Endpoints and Outcome Measures

Participants will be followed up at regular intervals over a 24-month period (see assessment schedule in 8.1). The primary outcome timepoint of interest is the 24-month follow point. Outcomes of interest are listed below:

Conversion to psychotic disorder. This is operationalised, as:

(A) At least one full threshold positive psychotic symptom as operationalised using the PSYCHS for one week or longer occurring (i) for more than an hour a day, 3-6 days per week OR (ii) daily for less than one hour

OR

(B) At least one full threshold positive psychotic symptom with the above frequency but lasting less than one week in the context of newly prescribed or newly increased antipsychotic medication

OR

(C) At least one full threshold positive psychotic symptom that is immediately dangerous – as assessed by the treating psychiatrist.

The projected number of converted cases across AMP SCZ is 300 (15% conversion rate)⁷.

*Remission of CHR status*⁷. The definition of remission from CHR status has previously been published⁸⁷ and is currently being used in our ongoing intervention trial²⁸. It is modelled on the schizophrenia course definitions presented by the Remission in Schizophrenia Working Group (RSWG)⁸⁸ and was agreed upon using a consensus process amongst CHR clinical and research experts. It requires no longer having attenuated psychotic symptoms in the CHR range, as assessed using the PSYCHS. For the Trait and State Risk Factor and Brief Limited Intermittent Psychotic Symptoms (BLIPS) groups, remission is defined as having achieved good functioning and no longer meeting criteria for schizotypal personality disorder (if present at baseline) and not having had onset of attenuated psychotic symptoms in the CHR range.

*Recovery from CHR status*⁷. Remission maintained for at least six months.

*Relapse of CHR status*⁷. Presence of CHR status after recovery (i.e., meeting PSYCHS severity, frequency and duration criteria for CHR status after recovery has been achieved).

Persistent non-psychotic disorders. A non-psychotic disorder which is present both at study entry and at outcome time point and from which full remission has not been achieved over

the interim. This will be determined using the Structured Clinical Interview for DSM-5 (SCID-5).

Incident non-psychotic disorders. A non-psychotic disorder present over the follow up period but not present at study entry. This will be determined using the SCID-5.

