5.5.2. Secondary outcomes

Secondary outcomes of interest are: remission, recovery and relapse of CHR status, psychosocial functioning, persistent and incident non-psychotic disorders, and persistent negative symptoms.

6. Study Design

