The Schedule of Assessments is shown in Section 8.1. An explanation of each measure can be found in the sections that follow. The aims of the research study will be best achieved if participants take part in *all* assessment components, as we are interested in building multimodal prediction models. Hence, participants must agree to participate in all assessments for which they are eligible. However, if a participant is ineligible to participate in a biomarker assessment (e.g., if they have braces and hence cannot undergo the MRI scan), they will still be able to participate in the study. The digital momentary assessments are an optional component of the study - participants can opt out of this component without compromising their participation in the overall study. The study visits may be split into multiple visits if this is preferred by the participant or the participant and their parent/legal guardian.

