8.3. Clinical Assessments

Informed by the recent advances in the field (see section 5.2), the study aims to collect multimodal data (clinical, biological, genetic, neurocognitive, neurophysiological, neuroimaging), baseline and repeat assessments over time ('macro' level monthly assessments) and 'micro-level' momentary (day-to-day) data collected through digital platforms (EMA and passive sensing). The 'macro' level repeat assessments are critical for both dynamic prediction of outcomes and also accurate characterization of clinical trajectories over time.

The battery of assessments are listed in 8.1 and described below. The selection of measures is informed by the Neurobiology in Youth Mental Health Partnership¹⁰¹, a national effort led by Orygen to standardize research assessments in order to create large datasets, guided by principles of feasibility, participant and clinical service burden, transdiagnostic relevance and translatability into clinical practice.

The following measures will be administered by RAs as part of an integrated clinical interview:

The **Positive Symptoms and Diagnostic Criteria for the CAARMS Harmonized with the SIPS (PSYCHS)** is a semi-structured interview which assesses symptoms associated with the prodromal phase of psychosis, and which is used to define the CHR criteria and onset of first-episode psychosis (FEP). The attenuated psychotic symptoms (positive symptoms) section of the PSYCHS will be assessed at all major assessment timepoints. This will be a rating of the worst period of each symptom either (1) over the last year (at Screener) or (2) since the participant's last research assessment.

The **Structured Clinical Interview for DSM-5 (SCID-5)** is a semi structured interview guide for determining DSM-5 diagnoses. The SCID-5-Research Version (RV)⁹⁷ will be used to assess DSM diagnostic criteria for Mood and Substance Use disorders and the SCID-5 Personality Disorders (PD)¹⁰² will be used to assess Schizotypal Personality disorder. If the participant converts to psychotic disorder, as determined using the PSYCHS, then the Psychotic Disorder section of the SCID-5-RV will be administered to determine type of DSM psychotic disorder. The language and diagnostic coverage

make the SCID-5 most appropriate for use with adults (age 18 and over); with slight modification to the wording of questions it may be used with adolescents.

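### CHR remission depends on a schizotypal personality disorder re-rating that Table 2 schedules only for controls, and section 8.3 names fewer SCID-5 disorder classes than the section 5.5 outcomes cover

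*Protocol*

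**What the plan says.** Protocol section 5.5.2 lists the secondary outcomes as "remission, recovery and relapse of CHR status, psychosocial functioning, persistent and incident non-psychotic disorders, and persistent negative symptoms", seven in all.

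**Remission.** For the Trait/State and BLIPS groups, section 5.5 sets three conditions: good functioning; no onset of attenuated psychotic symptoms in the CHR range; and, for those who had schizotypal personality disorder at baseline, ceasing to meet its criteria. Recovery is remission that has lasted six months or more. Relapse is a return of CHR status after recovery.

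**Non-psychotic disorders.** Section 5.5 defines the incident outcome as "A non-psychotic disorder present over the follow up period but not present at study entry. This will be determined using the SCID-5". The persistent outcome likewise names no class of disorder and uses the same instrument.

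**Instruments.** Section 8 says of the schedule that "An explanation of each measure can be found in the sections that follow". Section 8.3 then says that the SCID-5-RV "will be used to assess DSM diagnostic criteria for Mood and Substance Use disorders", adds its psychotic disorder section on conversion, and assigns schizotypal personality disorder to the SCID-5-PD. It gives no follow-up time point for the SCID-5-PD. It also says that the part of the PSYCHS rated at the major visits is the positive-symptom section.

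**Schedule.** In Table 2 the schizotypal module appears only in the inclusion/exclusion row. That row is marked for CHR participants and controls at screening, and for controls alone (C*) at M12 and M24. The SCID-5-RV has its own row.

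**The concern.** An outcome can be derived only if each of its components is measured when the outcome is rated. One component of remission is not scheduled for the participants to whom it applies, although it is scheduled twice for healthy controls, in whom remission has no meaning. This is a data-collection gap, so a later analysis plan could not recover an interview that never took place.

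For the disorder outcomes, the label is wider than the coverage that section 8.3 describes. Sites following 8.3 literally and sites reading 5.5 broadly could give different interviews, in data meant for pooling across two networks. These outcomes matter beyond the secondary list: the synopsis objective and section 5.4 commit the network to mapping "persistent and incident non-psychotic disorders, non-remission of CHR status, persistent negative symptoms, psychosocial functioning, full recovery".

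**Working it through.** The protocol gives no figure to reproduce here. The check sets the definitions against the schedule.

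**1. Remission in the Trait/State and BLIPS groups (section 5.5 against Table 2)**

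| Component | Table 2 source | CHR follow-up visits | Count |
|---|---|---|---|
| Attenuated symptoms | PSYCHS row | M1, M2, M3, M6, M12, M18, M24 | 7 |
| Functioning | SOFAS and GF row | M1, M2, M3, M6, M12, M18, M24 | 7 |
| Schizotypal personality disorder | Inclusion/exclusion row only | none | 0 |

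For controls, the third row has two follow-up visits, M12 and M24. The key to Table 2 defines C as healthy controls, and the starred footnote describes the control check-ins at those two months. PSYCHS and SOFAS share the inclusion/exclusion row but also have CHR follow-up rows of their own. The schizotypal module does not.

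**2. Could the PSYCHS stand in?** Not on the text. Section 8.3 limits the follow-up rating to positive symptoms, and the starred footnote lists the schizotypal assessment separately from the PSYCHS.

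**3. What depends on it.** Remission fails directly for participants with the disorder at baseline. Recovery requires remission, and relapse requires recovery. So 3 of the 7 secondary outcomes are touched, in this subgroup only.

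**4. Non-psychotic disorders (section 5.5 against section 8.3 and Table 2).** Table 2 schedules the SCID-5-RV for CHR participants at M0, M12, M18 and M24 (4 visits) and at conversion, so no visit is missing. Section 8.3 names two non-psychotic classes for it, mood and substance use; other classes, such as anxiety disorders, have none named. Screening questions followed by the section they point to are described in the Table 2 footnote for controls only. So 2 of the 7 secondary outcomes are touched, and only for disorders outside the two named classes.

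**5. Timing if the schizotypal module were added at M12, M18 and M24**

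- Affected subgroup: first possible remission rating M12; recovery no earlier than M12 + 6 months = M18; relapse no earlier than the next visit, M24.
- Other participants: first possible remission rating M1. M1 + 6 months = M7, and the next scheduled visit with both PSYCHS and functioning is M12, so recovery could be shown from M12 and relapse from M18.

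The delay is 11 months for a first remission rating (M12 − M1) and 6 months for recovery (M18 − M12) and for relapse (M24 − M18).

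**The case against.** Several points on the other side have force.

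- **The SCID-5 is scheduled.** A reader might infer that CHR participants lack SCID-5 follow-up altogether. Table 2 contradicts that: the SCID-5-RV is set at M0, M12, M18, M24 and conversion. The gap is in the coverage stated in section 8.3, and mood and substance use outcomes can be derived as planned.
- **Section 8.3 does not say only.** Elsewhere the protocol marks restrictions openly, as it does for the abbreviated FIGS and the two-subtest IQ measure. Section 8.3 may therefore be incomplete rather than restrictive, and it does not show that other disorders would be missed. What stands is that 8.3 is where the measure is meant to be explained, and it names two classes for an outcome without limit.
- **Anxiety as a promised outcome.** The synopsis rationale refers to "other clinical outcomes (e.g., non-remission of CHR status, functioning, anxiety, depression, and substance use disorders", and section 5.1.1 has similar wording. It is tempting to infer that the study promised SCID-5 anxiety diagnoses. These are programme-level aims, not outcome definitions, and they do not require a diagnostic interview. Anxiety severity is rated by OASIS in CHR participants, although that is not a SCID-5 diagnosis. Likewise, the mention in section 5.2 of "persistent and incident non-psychotic disorders, non-remission of CHR status, poor functioning etc" is background and defines no study outcome.
- **Absence from Table 2 is imperfect evidence.** The table as read has no row for the NSI-PR, although section 8.3 says it will be given and section 5.5 uses it. The table may be incomplete as written, or a row may have been lost in reading. This weakens the inference somewhat. It does not remove it: the schizotypal module is present in the table, with follow-up marks for controls and none for CHR participants, and section 8.3 supplies no other time point.

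**Conclusion.** The point holds in two parts of unequal weight, and the sections should be corrected.

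The main part is that, for Trait/State or BLIPS participants with schizotypal personality disorder at baseline, remission cannot be rated as defined from the stated schedule, and neither can recovery or relapse. The protocol gives no rate for this subgroup, so neither a count nor a claim that it is small or large can be supported. Participants in those groups without the disorder at baseline are not affected.

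The lesser part is a mismatch of scope. The persistent and incident outcomes are unlimited in 5.5, while 8.3 names mood and substance use only. This calls for clarification and is not a demonstrated loss of diagnoses.

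Conversion to psychosis (the primary outcome), functioning by SOFAS, and mood and substance use diagnoses are unaffected. The conclusion assumes that Table 2 and section 8.3 state the CHR assessments in full. If a study manual already provides the missing interviews, the protocol text still needs correcting.

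**What to change.** **Remission.** Reconcile section 5.5 with Table 2 by one of two routes.

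- Add the schizotypal module at M12, M18 and M24 for CHR participants positive at screening, and state that remission in this subgroup is rated at those visits. The cost is interview time at three visits already scheduled. It also puts two time scales inside one outcome, since remission could be rated only from M12 in this subgroup against M1 in others; recovery could not be shown before M18, nor relapse before M24.
- Revise the remission definition so that it uses only instruments scheduled for CHR participants at follow-up. This adds no interview, but the definition would depart from the published one that section 5.5 cites, and the schizotypal condition would be lost.

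**Non-psychotic disorders.** Again there are two routes.

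- State in section 8.3 which SCID-5 sections CHR participants receive at M0, M12, M18 and M24. The screen-then-section procedure already written for controls is one model. The cost is interview time if coverage widens.
- Relabel the outcomes as persistent or incident mood or substance use disorder in five places: the synopsis objectives and sections 5.4, 5.5, 5.5.2 and 17. The cost is a narrower outcome. Section 5.2 is background and can stay as it is.

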Persistent negative symptoms (PNS). As per our previous research⁸⁹, and consistent with the definition of Buchanan⁹⁰, PNS are defined as the presence of at least one Negative Symptoms Inventory (NSI) global subscale score ≥ 3 at baseline and at follow up, a combined total score of 6 or less on the Brief Psychiatric Rating Scale (BPRS) subscales of depression, guilt and suicidality (corresponding to an average of “very mild” or less on each item), and a combined total score of 16 or less on the BPRS psychotic subscales of conceptual disorganisation, hallucinations, suspiciousness and unusual thought content (corresponding to an average of “moderate” or less on each item).

Psychosocial functioning. SOFAS score at outcome time points.

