8.1. Table 2 Schedule of Assessments

✓ = CHR participants

C = HC participants (70 HCs - 20 from Melbourne, 5 from each of the other sites/hubs, will receive the repeat assessments at month 2 follow up)

		V1	V2	V3	V4	V5	V6	V7	V8	V9	V10	V11	V12	V13	V14	V15	V16	Conversion
Domain	Instrument/ Specimen	Screening	M0	M1	M2	M3	M4	M5	M6	M7	M8	M9	M10	M11	M12	M18	M24	
Informed consent																		
CLINICAL																		
Inclusion/Exclusion criteria	PSYCHS/SOFAS/SCID5-PD-Schizotypal /FIGS (abbreviated version)/ TBI/medication use (PharmaTreat)	✓C													C*		C*	
Medical & psychiatric history	Health and Medical Conditions Questionnaires	✓C	✓	✓	✓C	✓	✓	✓	✓	✓	✓	✓	✓	✓	✓C	✓	✓C	
Demographics	Demographics		✓C															
Premorbid functioning	PAS			✓														
Adverse events	Adverse Events		✓C	✓C	✓C	✓C	✓C	✓C	✓C	✓C	✓C	✓C	✓C	✓C	✓C	✓C	✓C	
Attenuated psychotic symptoms, associated distress, and conversion to psychosis	PSYCHS		✓C	✓	✓C	✓			✓						✓C*	✓	✓C*	✓C
General psychopathology	BPRS ⁹⁴		✓C	✓	✓C	✓	✓	✓	✓	✓	✓	✓	✓	✓	✓	✓	✓	
Depression	CDSS		✓C	✓	✓C	✓			✓						✓	✓	✓	
Anxiety	OASIS ⁹⁵		✓C	✓	✓C	✓			✓						✓	✓	✓	
Suicidality	CSSRS		✓C		✓C				✓						✓	✓	✓	

		V1	V2	V3	V4	V5	V6	V7	V8	V9	V10	V11	V12	V13	V14	V15	V16	Conversion
Sleep disturbance	PROMIS-SD		✓C		✓C				✓						✓	✓	✓	
Substance use	ASSIST ⁹⁶		✓C		✓✓				✓						✓	✓	✓	
DSM diagnoses	SCID-5-RVs ⁹⁷		✓C												✓C*	✓	✓C*	✓C
Patient global impression of severity	PGI-S		✓C	✓	✓C	✓			✓						✓	✓	✓	
Psychosocial functioning	SOFAS ⁹⁸ , GF Social, GF Role		✓C	✓	✓C	✓			✓						✓C*	✓	✓C*	✓C
Perceived Stress Scale	PSS		✓C	✓	✓C	✓			✓						✓	✓	✓	
Perceived Discrimination Questionnaire	PDQ		✓C															
Pubertal development Scale	PDS		✓C															
Psychosis Polyrisk Score	PPS ⁹⁹		✓C															
DIGITAL MOMENTARY ASSESSMENTS																		
Daily changes in mental state and context	EMA		✓C	✓C	✓C	✓C	✓C	✓C	✓C	✓C	✓C	✓C	✓C	✓C	✓C			
Physical activity, sleep-wake cycles, travel patterns	Passive sensing (actigraphy, geolocation)		✓C	✓C	✓C	✓C	✓C	✓C	✓C	✓C	✓C	✓C	✓C	✓C	✓C			
NEUROCOGNITION																		
Premorbid IQ	WRAT 5 Reading Accuracy		✓C															
		V1	V2	V3	V4	V5	V6	V7	V8	V9	V10	V11	V12	V13	V14	V15	V16	Conversion
Current IQ	WASI-II - 2-subtest version (Vocab & MR) ¹⁰⁰		✓C														✓	
Processing speed	Digit-Symbol Substitution Test		✓C		✓C				✓						✓		✓	

		V1	V2	V3	V4	V5	V6	V7	V8	V9	V10	V11	V12	V13	V14	V15	V16	Conversion
Attention	Continuous Performance Test		✓C		✓C				✓						✓		✓	

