Family Interview for Genetic Studies (FIGS)¹⁰³: The FIGS, developed by NIMH, is an instrument that gathers diagnostic information on families in genetic and family studies on mental disorders, such as schizophrenia and bipolar disorders. It offers diagnostic information on each family member of the study participant. The FIGS has been found to be valid and reliable and has been used extensively in previous research. An abbreviated version will be used in the current study, limiting assessment of family history of mental disorder to psychotic, mood and substance use disorders.

The **Social and Occupational Functioning Assessment Scale (SOFAS)**⁹⁸ is a numeric scale (1 through 100) used to rate social and occupational functioning. The SOFAS focuses exclusively on the individual's level of social and occupational functioning, not symptom severity.

The **Global Functioning: Social and Role scales (GF:S and GF:R)**¹⁰⁴ will also be used to rate social and role functioning.

Premorbid Adjustment Scale (PAS): The PAS will be used to assess premorbid functioning across developmental periods and across a number of domains. Each domain is rated on a 0 to 6 point scale, with 0 indicating normal adjustment and 6 indicating severe impairment. The “premorbid” period for PAS purposes is the period ending six months prior to the participant first meeting CHR criteria.

The **Brief Psychiatric Rating Scale (BPRS)**⁹⁴ is a rating scale in which 24 items relating to different types of psychopathology are rated on a continuum of not present to extremely severe. This measure will provide an overall measure of general psychopathology.

The **Negative Symptom Inventory-Psychosis Risk (NSI-PR)**¹⁰⁵. The NSI-PR was designed specifically for measuring negative psychotic symptoms in the CHR population, taking into account aspects of behaviour and socialization that are common to this age range.

The **Overall Anxiety Severity and Impairment Scale (OASIS)**⁹⁵ is a valid and reliable measure of anxiety severity and related impairment. It is a brief (five-item) continuous measure, which can be used across anxiety disorders, with multiple anxiety disorders, and with subthreshold anxiety symptoms. The total OASIS score is calculated by adding together the scores for the five questions. A score of 8 or above suggests clinically significant anxiety.

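### Persistent negative symptoms is a secondary outcome scored on the Negative Symptom Inventory at baseline and follow-up, but the Schedule of Assessments gives that instrument no visit

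*Protocol*

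**What the plan says.** Section 5.5 requires, for persistent negative symptoms, "at least one Negative Symptoms Inventory (NSI) global subscale score ≥ 3 at baseline and at follow up". It adds two BPRS conditions: "a combined total score of 6 or less on the Brief Psychiatric Rating Scale (BPRS) subscales of depression, guilt and suicidality", and a total of 16 or less on four psychotic items. Section 5.5.2 lists the outcome among the secondary ones: "persistent and incident non-psychotic disorders, and persistent negative symptoms". It is also one of the outcomes that Aim 1 (section 5.4) sets out to map over two years. On timing, section 5.5 says: "The primary outcome timepoint of interest is the 24-month follow point".

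Section 8.3 states "The battery of assessments are listed in 8.1 and described below" and then "The following measures will be administered by RAs as part of an integrated clinical interview". The NSI-PR is among the measures that follow: "The NSI-PR was designed specifically for measuring negative psychotic symptoms in the CHR population". Its paragraph gives no visit. The synopsis entry on study endpoints likewise sends the reader to section 8.1 for each endpoint. Section 8.1, "Table 2 Schedule of Assessments", contains no entry for the NSI or NSI-PR, either in its rows or in its notes.

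**The concern.** An outcome defined by persistence needs the same measurement at two times. The protocol makes Table 2 the place where visits are fixed, and the one instrument that defines this outcome is not in it. A research assistant following the table at M0 would not give the interview, and nothing done later can supply a baseline score.

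Three things are at stake:

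- **The outcome itself.** Without a baseline NSI-PR score a participant cannot be classified.
- **Comparability between sites.** The study has 11 centres. Those that notice section 8.3 and add the interview must choose the visits themselves, so availability and timing of the score would depend on site.
- **Prediction models.** Section 14 describes the candidate predictors by reference to the assessments in section 8.1. An instrument that is not listed there has no clear place among them.

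Monitoring is also weakened. Section 13.3.1 counts missed assessments as protocol deviations, but an assessment with no scheduled visit cannot be flagged as missed.

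**Working it through.** No sample size, power or event figure is involved, so the check is a comparison of sections.

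**1. What the definition needs.** Section 5.5 needs an NSI global subscale score at baseline and again at follow-up, so at least 2 administrations per participant. It also needs the BPRS items.

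**2. What Table 2 schedules.** The table has 16 numbered visits (V1 screening, V2 = M0, through V14 = M12, V15 = M18, V16 = M24) and a conversion column.

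| Component of the definition | Instrument | Scheduled visits, CHR participants |
|---|---|---|
| Negative-symptom score | NSI / NSI-PR | 0 of 16, and not at conversion |
| Depression, guilt, suicidality limit | BPRS | 15 of 16 (V2 to V16) |
| Psychotic-item limit | BPRS | 15 of 16 (V2 to V16) |

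The limits that restrict the definition can be collected at every visit from baseline on. The score that establishes it is collected at none.

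**3. Whether other text supplies the visits.** The notes to Table 2 do not mention the instrument. Section 6.4 gives visit durations and names no negative-symptom scale. Section 8.3 describes the NSI-PR without a time point.

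**4. Whether another scheduled measure could stand in.** Section 8.3 says it is the attenuated (positive) symptom section of the PSYCHS that is assessed at the major time points. The BPRS enters the definition only through its two limits. Section 5.5 names no substitute for the NSI score.

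**5. Whether the table is generally incomplete.** Each measure in sections 8.3 and 8.4 was looked for in Table 2.

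- Section 8.3: PSYCHS, SCID-5, FIGS, SOFAS, Global Functioning scales, PAS, BPRS, OASIS, PROMIS-SD, CDSS, ASSIST and CSSRS are present (12). The NSI-PR is absent.
- Section 8.4: PGI-S, PSS, perceived discrimination, pubertal development and PPS are present (5).

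So 12 + 5 = 17 of the 18 described measures have a place in the table. The NSI-PR is the single exception.

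**6. Naming.** Section 5.5 uses Negative Symptoms Inventory (NSI), while section 8.3 uses Negative Symptom Inventory-Psychosis Risk (NSI-PR). These appear to be the same instrument, but the protocol does not say so.

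**The case against.** The strongest reply is that the protocol, read as a whole, already commits to the measure. Section 8.3 says research assistants will administer it, section 5.5 says baseline is needed, and section 5.5 also puts the main interest at 24 months. On this reading only a table row is missing, and sites also have a procedures manual and electronic case report forms that may schedule the interview. This has some force: the instrument is not absent from the protocol, and loss of the outcome is conditional on sites working from Table 2. It does not remove the fault. No section states the visits, section 8.3 itself refers to section 8.1 for the battery, and documents not at hand neither cure nor confirm the gap.

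A second reply is that the table was read by a program from a PDF and a row may have been lost. That cannot be excluded entirely. The informed-consent row, for example, shows no mark at any visit, and the clinical block breaks across a page. Against this, all 17 other described measures came through. The abbreviation list has no NSI entry either, but it also omits PAS, PSS, PPS and PROMIS-SD, all of which are in Table 2, so it is not evidence one way or the other.

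A third reply is that only a secondary outcome is affected and that visit rules for it could sit in an analysis plan. The first half is right. The second is not: an analysis plan can choose among collected visits but cannot schedule data collection.

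**Conclusion.** The concern holds. Sections 5.5 and 8.3 rely on an instrument that section 8.1 gives at 0 of 16 numbered visits, where at least 2 are required. If Table 2 is followed as written, one named secondary outcome cannot be derived for any of the 937 CHR participants. If some sites add the interview on their own reading of section 8.3, the outcome becomes dependent on site.

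This rests on two assumptions: that Table 2 as read is complete, and that sites take visit timing from it, as the protocol directs. The conversion outcome, assessed with the PSYCHS, and the sample size argument in section 7.2 are untouched. The fault is an internal inconsistency rather than a deliberate design choice, but it must be corrected because the missing baseline score is not recoverable: any participant who passes M0 without it stays unclassifiable.

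**What to change.** - Add an NSI-PR row to Table 2 for CHR participants, marked at M0 and at each follow-up visit on which PNS will be judged, including M24. The BPRS is already scheduled at all of these, so both parts of the definition would then be collected together.
- State in section 5.5 which visit or visits the follow-up half of the definition refers to.
- Use one name for the instrument in sections 5.5, 8.1 and 8.3.
- If the manual or case report forms already schedule the interview, make Table 2 agree with them.

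The cost is one table row, one sentence and the rater time at the named visits, for an interview that section 8.3 already commits the study to giving.
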